## 5.2 Exclusion Criteria

1. Within 6 months of Screening: acute coronary syndrome, major cardiac surgery, or stroke/transient ischemic attack
2. Within 3 months of Screening: coronary or peripheral arterial revascularization, major non-cardiac surgery, or lipoprotein apheresis
3. Heart failure New York Heart Association (NYHA) class IV
4. Uncontrolled hypertension (systolic > 160 or diastolic > 100 mm Hg)
5. History of acute kidney injury within 12 months of Screening
6. Uncontrolled hyper or hypothyroidism
7. Active infection requiring systemic antiviral or antimicrobial therapy that will not be completed prior to Study Day 1
8. Known history of or positive test for human immunodeficiency virus (HIV), hepatitis C or chronic hepatitis B
9. Malignancy within 5 years, except for basal or squamous cell carcinoma of the skin or carcinoma *in situ* of the cervix that has been successfully treated

10. Patients with a history of major bleed or high-risk of bleeding diathesis
11. Recent history of, or current drug or alcohol abuse
12. Clinically-significant abnormalities in screening laboratory values that would render a patient unsuitable for inclusion, including the following:
  - a. Urine protein/creatinine ratio (UPCR)  $\geq 0.25$  mg/mg. In the event of a UPCR above this threshold, eligibility may be confirmed by a quantitative total urine protein measurement of  $< 300$  mg/24-hr
  - b. Urine albumin/creatinine ratio (UACR)  $\geq 100$  mg/g. In the event of a UACR above this threshold, eligibility may be confirmed by a quantitative total urine albumin measurement of  $< 150$  mg/24-hr
  - c. Estimated GFR  $< 60$  mL/min (as determined by the Chronic Kidney Disease-Epidemiological Collaboration (CKD-EPI) Equation for creatinine clearance
  - d. Alanine aminotransferase (ALT) or aspartate aminotransferase (AST)  $> 2.0 \times$  ULN
  - e. Bilirubin  $>$  ULN, unless prior diagnosis and documentation of Gilbert's syndrome in which case total bilirubin must be  $\leq 3$  mg/dL
  - f. Alkaline phosphatase (ALP)  $>$  ULN
  - g. Platelet count  $<$  LLN
13. Use of warfarin, direct thrombin inhibitors or factor Xa inhibitors
14. Treatment with another investigational drug, biological agent, or device within 1 month of Screening, or 5 half-lives of investigational agent, whichever is longer
15. Treatment with any non-Ionis oligonucleotide (including small interfering ribonucleic acid [siRNA]) at any time or prior treatment with an Ionis oligonucleotide or siRNA within 9 months of screening. Patients that have previously received only 1 dose of an Ionis oligonucleotide as part of a clinical study may be included as long as  $\geq 4$  months has elapsed since dosing
16. BMI  $> 40$  kg/m^2
17. Blood donation of 50-499 mL within 30 days of Screening or of  $> 499$  mL within 8 weeks of Screening
18. Unwillingness to comply with study procedures, including follow-up, as specified by this protocol, or unwillingness to cooperate fully with the Investigator
19. Have any other conditions, which, in the opinion of the Investigator or Sponsor would make the patient unsuitable for inclusion, or could interfere with the patient participating in or completing the Study

## 6. STUDY PROCEDURES

### 6.1 Study Schedule

All required study procedures are outlined in [Appendices A, B, and C](#).

#### 6.1.1 Screening

Written informed consent for the study will be obtained prior to the performance of any study-related procedures including screening procedures. A 4-week period is provided for completing screening assessments and determining patient eligibility for the study. Abnormal screening results may be re-tested once for determination of patient eligibility after consultation with the Sponsor Medical Monitor. Patients may be re-screened 1 time in order to determine eligibility.

During the screening period, patients will undergo a medical history and physical examination including vital signs, 12-lead electrocardiogram (ECG) and have blood and urine samples taken for clinical laboratory testing. Patients will be screened for HIV, hepatitis B, and hepatitis C.

On confirmation of eligibility and prior to randomization, patients will also undergo a 24 hr urine collection for creatinine, albumin, and protein as a baseline assessment.

#### 6.1.2 Treatment Period

During the treatment period, patients will report to the study center for clinic visits. Patients will receive 20 mg doses of Study Drug administered by SC injection once every 4 weeks for up to 52 weeks in Cohort A, 40 mg doses of Study Drug administered by SC injection once every 4 weeks for up to 52 weeks in Cohort B, 60 mg doses of Study Drug administered by SC injection once every 4 weeks for up to 52 weeks in Cohort C, 20 mg doses of Study Drug administered by SC injection once every 2 weeks for up to 52 weeks in Cohort D, or 20 mg doses of Study Drug administered by SC injection once per week (weekly) for up to 52 weeks in Cohort E ([Section 8.1](#)).

Collection and measurement of vital signs, physical examination results, ECGs, clinical laboratory parameters (Appendix B), ISIS 681257 plasma concentrations, immunogenicity and biomarker samples, AEs and concomitant medication/procedure information will be performed according to the Schedule of Procedures in Appendix A.

#### Extensive Pharmacokinetic (PK) Subgroup Only:

Within each cohort, a subgroup of approximately 12 patients, who will consent to extensive PK sampling, will undergo additional PK sampling, in what is referred to as the PK Subgroup in this study. Patients in this subgroup will have additional PK sampling time points in order to evaluate the plasma PK parameters of ISIS 681257. Patients in this subgroup will have additional visits to the clinic during the treatment period in order to collect blood samples for PK assessment (Appendix C).

#### 6.1.3 Post-Treatment Period

Each patient will be followed for safety assessments for 16 weeks after the last dose of Study Drug. During the post-treatment follow-up period, patients will return to the Study Center

for 3 outpatient visits at Weeks 4, 10, and 16 after the last dose of Study Drug for safety and clinical laboratory evaluations and for blood sampling for PK ([Appendices A and C](#)).

## 6.2 Additional Study Assessments

### 6.2.1 Laboratory Assessments

Laboratory analyte samples will be collected throughout the study. A list of these analytes is contained in [Appendix B](#).

Routine blood chemistry and urine samples (excluding 24-hour urine collection) should be taken after fasting for at least 10 hours. Any confirmatory test, or test taken for safety reasons, may be taken at any time, irrespective of fasting status. During preparation for fasting samples, the patient can drink water and they should ensure that they consume sufficient water in order to not become dehydrated.

If tests are uninterpretable (e.g., due to clumping, hemolysis or quantity not sufficient) or missing, a repeat blood or urine specimen should be re-drawn as soon as possible (ideally within 1 week).

Hematology samples will be collected every 14 days. Each time a hematology lab is drawn and sent to the central laboratory for analysis, an additional sample must be collected in parallel and analyzed locally. In the event that both the central and local samples are unreportable (e.g., due to hemolyzed or clumped blood samples), patient dosing cannot continue until another sample is repeated and determined not to have met a platelet stopping rule.

If there is no reportable platelet count within 14 days of the last platelet count, the Investigator will contact the patient to hold dosing until a new platelet count is obtained and reviewed.

Blood and urine samples for renal function testing will also be collected every 14 days and sent to the central laboratory for analysis, per [Section 8.5.2](#). If there are no test results available within 14 days of the last set of results for parameters considered critical to patient safety, the Investigator will contact the patient to hold dosing until a new test set is obtained and reviewed.

Liver function testing will also be collected every 14 days and sent to the central laboratory for analysis for the first 3 months of the study treatment, and monthly thereafter during the Treatment Period per [Section 8.5.1](#).

All lab samples sent to the central laboratory are received on the next day and processed. Lab Alerts issued as per protocol safety monitoring requirements or stopping rules will indicate the applicable protocol section to facilitate review and will be immediately and simultaneously sent by email to the Investigator, the Sponsor and the CRO Medical Monitors, the Sponsor Drug Safety Physician, and the Clinical Trial Manager (CTM), and should be received by them within 2 days from sample collection. Hematology results from the site's local laboratories are received by the study center staff on the day of sample collection, and should be entered as soon as possible into the eCRF to inform the Sponsor and CRO study monitoring teams.

All platelet count results must be reviewed promptly (within 48 hours of receipt) by the Investigator, or designee, to ensure that the count has not met the stopping rule and to determine

whether the rate of decline is suggestive that the patient could be approaching the dose interruption rule of 75,000/mm^3 as specified in [Section 8.6.3](#). Any case of a platelet count reduction to levels below 50,000/mm^3 (Grade 3 or Grade 4) is considered an adverse event of special interest and must be reported in an expedited fashion to the Sponsor as per [Sections 9.3.3.1](#) and [9.4.1](#).

All liver and renal function tests must also be reviewed promptly (within 48 hours of receipt) by the Investigator, or designee, to ensure that the result has not met the stopping rule.

All lab alerts received, including those related to platelet, liver, or renal function monitoring/stopping rules, are also reviewed promptly by the Sponsor and the CRO Medical Monitors who will agree on actions to be taken. Within 24 hours of receiving an actionable lab alert the CRO Medical Monitor will communicate instructions to the Investigator and the study personnel by emailing them the Safety Surveillance Form that needs to be signed by the Investigator/study personnel and promptly returned to the Sponsor and CRO Medical Monitor. In urgent cases, such as platelets results below 50,000/mm^3, or liver or renal test results reaching a critical stopping rule the Investigator must also be contacted by phone.

Further information on safety monitoring and actions to be taken by the Study Investigator in the event of reduced platelet count are provided in [Sections 8.5.3](#) and [8.6.3](#).

### **6.2.2 Physical Exams and Vital Signs**

Physical exams and vital signs will be performed as indicated in the Schedule of Procedures ([Appendix A](#)). Vital signs should include weight, blood pressure (BP), pulse rate, respiratory rate and body temperature. BP and pulse rate will be recorded after the patient has been in a sitting position for at least 5 minutes. BP should always be measured on the same arm (preferentially on the left arm). Height will be measured at Screening.

### **6.2.3 Electrocardiography**

Electrocardiography (ECG) will be conducted at Screening, Day 1, (prior to the first dose of Study Drug), and again during the treatment period as follows per dosing cohort:

- Cohorts A, B, and C at Weeks 5, 13, 21, 25, 33, 41, 49, and 53
- Cohorts D and E at Weeks 5, 13, 21, 27, 33, 41, 49, and 53

In all cohorts, ECGs will be conducted during the post-treatment follow-up period at 4, 10, and 16 weeks after the last dose of Study Drug.

ECGs will be recorded after the patient has been resting in a supine position for at least 5 minutes. ECGs will be performed in triplicate.

### **6.2.4 PK Sampling**

Blood samples for the determination of plasma ISIS 681257 concentrations will be collected prior to dosing on Day 1 and at various times throughout the treatment and post-treatment follow-up periods as noted in the tables in [Appendix C](#).

Within each cohort, patients assigned to the PK Subgroup will have additional PK sampling time points and additional visits to the clinic during the treatment period in order to collect blood samples for PK assessment ([Appendix C](#)).

### 6.3 Restriction on the Lifestyle of Patients

#### 6.3.1 Contraception Requirements

All male patients and women of childbearing potential must refrain from sperm/egg donation and either be abstinent† or practice effective contraception from the time of signing the informed consent form until at least 16 weeks after their last dose of study treatment.

Male patients engaged in sexual relations with a female of child-bearing potential must also encourage their female partner to use effective contraception from the time of signing the informed consent until 16 weeks after the patient's last dose of study treatment.

For the purposes of this study, women of childbearing potential are defined as any female who has experienced menarche, and who does not meet 1 of the following conditions:

- Postmenopausal: 12 months of spontaneous amenorrhea in females > 55 years of age or, in females ≤ 55 years, 12 months of spontaneous amenorrhea without an alternative medical cause and FSH levels in the postmenopausal range for the laboratory involved
- 6 weeks after surgical bilateral oophorectomy with or without hysterectomy
- Post hysterectomy

For the purposes of the study, effective contraception is defined as follows:

For male patients:

- Effective male contraception includes a vasectomy with negative semen analysis at Follow-up, or the use of condoms together with spermicidal foam/gel/film/cream/suppository
- Male patients with partners that are pregnant must use condoms as contraception to ensure that the fetus is not exposed to the Study Drug

For female patients and female partners of male patients:

- Using 1 or more of the following acceptable methods of contraception: surgical sterilization (e.g., bilateral tubal ligation), hormonal contraception, intrauterine contraception/device, or any 2 barrier methods (a combination of male or female condom\* with diaphragm, sponge, or cervical cap) together with spermicidal foam/gel/film/cream/suppository

†**Note:** Abstinance is only acceptable as true abstinence, i.e., when this is in line with the preferred and usual lifestyle of the patient. Periodic abstinence (e.g., calendar, ovulation, symptothermal, post-ovulation methods), declaration of abstinence for the duration of a trial and withdrawal are not acceptable methods of contraception.

**\*Note: A female condom and a male condom should not be used together as friction between the 2 can result in either or both products failing.**

### 6.3.2 Other Requirements

All patients will be required to fast for at least 10 hours before visits requiring fasted blood sampling.

## 7. STUDY DRUG

### 7.1 Study Drug Description

Study Drug (ISIS 681257 or Placebo) characteristics are listed in Table 1.

Study Drug (ISIS 681257 or Placebo) will be provided as 0.8 mL deliverable volume in 2 mL stoppered and sealed glass vials as a sterile solution.

The Study Drug is clear to slightly yellow in color, it is for single use, contains no preservatives and must be stored between 2 to 8 °Celsius and be protected from light.

#### 7.1.1 ISIS 681257

ISIS 681257 vials contains 100 mg/mL ISIS 681257 in Water for Injection. Additionally, sodium phosphate buffer and sodium chloride are added to control the measure of the acidity or basicity of the solution (pH) and tonicity, respectively. The target pH is 7.4.

#### 7.1.2 Placebo

Placebo vials contain 0.9% sodium chloride in Water for Injection. 1.6 µg/mL riboflavin is added to ensure color matching of placebo vials to ISIS 681257 vials.

**Table 1 Study Drug Characteristics**

Study Drug	ISIS 681257	Placebo
Strength	100 mg/mL	Not Applicable
Volume/Formulation	0.8 mL solution per 2.0 mL vial	0.8 mL solution per 2.0 mL vial
Route of Administration	SC	SC

SC = subcutaneous

### 7.2 Packaging and Labeling

The Sponsor will provide the Investigator with packaged Study Drug (ISIS 681257 or placebo) labeled in accordance with specific country regulatory requirements.

### 7.3 Study Drug Accountability

The study staff is required to document the receipt, dispensing, and return of Study Drug (ISIS 681257 or placebo) supplies provided by the Sponsor. The patient must return all used and unused Study Drug to the Study Center for accountability. The Study Center must return all

used and unused Study Drug to the Sponsor or designee for destruction. All used syringes must be disposed of as per the site's hazardous waste destruction policy.

## **8. TREATMENT OF PATIENTS**

### **8.1 Study Drug Administration**

ISIS 681257 will be administered to patients by Study Center staff as follows:

- Cohort A: a single SC dose of 20 mg once every 4 weeks for up to 52 weeks and a maximum of 13 doses
- Cohort B: a single SC dose of 40 mg once every 4 weeks for up to 52 weeks and a maximum of 13 doses
- Cohort C: a single SC dose of 60 mg once every 4 weeks for up to 52 weeks and a maximum of 13 doses
- Cohort D: a single SC dose of 20 mg every 2 weeks for up to 52 weeks and a maximum of 26 doses
- Cohort E: a single SC dose of 20 mg every week (weekly) for up to 52 weeks and a maximum of 52 doses

Self-administration will be allowed after appropriate training of patient and/or caregiver.

Patients in Cohorts A, B, and C should receive 1 dose every 4 weeks, patients in Cohort D should receive 1 dose every 2 weeks and Cohort E should receive 1 dose per week with weeks always defined relative to Study Day 1. For example if a patient receives the first dose on a Monday, subsequent doses should be given on Mondays according to the respective dosing schedule, if possible. If a patient misses an injection, or if dosing on the usual day is not possible, the patient can reschedule the injection provided that 2 doses are administered at least 2 days apart.

Every effort should be made to ensure the previous dose is given 7 days prior to a scheduled clinic visit.

Please refer to the Study Drug Manual provided by the Sponsor or designee for more detailed instructions for Study Drug (ISIS 681257 or placebo) preparation and administration.

**Table 2 Study Drug Dosing Information**

Cohort	Treatment	Volume to Administer/Dose	# Doses	Total ISIS 681257
A	20 mg ISIS 681257 or placebo (Every 4 weeks)	0.2 mL	≤ 13	≤ 260 mg
B	40 mg ISIS 681257 or placebo (Every 4 weeks)	0.4 mL	≤ 13	≤ 520 mg
C	60 mg ISIS 681257 or placebo (Every 4 weeks)	0.6 mL	≤ 13	≤ 780 mg
D	20 mg ISIS 681257 or placebo (Every 2 weeks)	0.2 mL	≤ 26	≤ 520 mg
E	20 mg ISIS 681257 or placebo (Every week)	0.2 mL	≤ 52	≤ 1040 mg

## 8.2 Other Protocol-Required Drugs

No other Study Drug treatments are required by the protocol.

## 8.3 Other Protocol-Required Treatment Procedures

No other treatment procedures are required by the protocol.

## 8.4 Treatment Precautions

No specific treatment precautions are required.

## 8.5 Safety Monitoring Rules

Please refer also to the “Guidance for Investigator” section of the Investigator’s Brochure.

For the purposes of safety monitoring baseline is defined as the average of the pre-dose test closest to Day 1 and the Day 1 value itself.

In addition to the standard monitoring of clinical safety parameters, the following guidelines are provided for the monitoring of selected parameters chosen based on preclinical and clinical observations.

In case of discrepancy between the test results from 2 sources, such as between the central and local lab, safety-mandated action must be initiated based on the more critical (lower or higher, as relevant) of the 2 values.

Confirmation Guidance: At any time during the study (treatment or post-treatment follow-up periods), the clinical laboratory results meeting any of the safety monitoring criteria presented below **must be confirmed** by performing measurements (ideally in the same laboratory that performed the initial measurement) on new specimens prior to administering the next dose of

Study Drug (ISIS 681257 or placebo). All new specimen collections should take place as soon as possible (ideally within 3 days of the initial collection).

In addition, as described in [Section 6.2.1](#) hematology labs should be sent in parallel to the central and local laboratory for analysis.

Stopping Rule Guidance: The Investigator may interrupt or permanently discontinue study treatment for any medical reason including changes in clinical laboratory results.

In the event of an initial clinical laboratory result that meets a stopping criterion, patients must not be re-dosed until a confirmatory test result has been reviewed by the Study Medical Monitor. If any of the stopping criteria described below (refer to [Sections 8.6.1](#) to [8.6.3](#)) are met and are confirmed, the patient will be permanently discontinued from further treatment with Study Drug (ISIS 681257 or placebo), evaluated fully as outlined below and in consultation with the Study Medical Monitor or appropriately qualified designee, and will be entered into the post-treatment evaluation portion of the study. In general, patients who do not meet the stopping rules based upon retest may continue dosing. However, the Investigator and the Study Medical Monitor (or appropriately qualified designee) should confer as to whether additional close monitoring of the patient is appropriate.

Additional Guidance: If possible, a PK sample should be collected as soon as possible after an SAE has occurred (preferably within 2 weeks). In addition, if a patient is asked to return to the clinic for additional evaluations due to an AE, then a PK sample should be taken at the time of the unscheduled visit.

### **8.5.1 Safety Monitoring Rules for Liver Chemistry Tests**

The following rules are adapted from the FDA guidance for industry, “Drug-Induced Liver Injury: Premarketing Clinical Evaluation,” issued by the U.S. Department of Health and Human Services, Food and Drug Administration, July 2009. For a definition of Baseline, please refer to guidance in [Section 8.5](#) above.

All patients will have liver chemistry tests monitored every 2 weeks for the first 3 months of the study treatment, and monthly thereafter during the Treatment Period.

In the event of appearance of symptoms or signs of hepatic injury (jaundice, fatigue, nausea, vomiting, right upper quadrant pain or tenderness, fever, rash, abnormal bleeding or bruising, or eosinophilia > ULN) liver enzymes and bilirubin should be tested as soon as possible. Testing at a lab that is local to the patient is permissible for this purpose.

In the event of an ALT or AST measurement that is > 3 x ULN (or the greater of 2 x baseline value or 3 x ULN if the baseline value was > ULN) at any time during the study (treatment or post-treatment period), the initial measurement(s) should be confirmed as described in [Section 8.5](#).

Patients with confirmed ALT or AST levels > 3 x ULN should have their liver chemistry tests (ALT, AST, ALP, international normalized ratio [INR] and total bilirubin) retested at least once weekly until ALT and AST levels become  $\leq 1.2$  x ULN.

All results of liver function tests must be reviewed promptly (within 48 hours of receipt) by the Investigator or the designee to ensure that the result has not met the stopping rules per [Section 8.6.1](#).

Further Investigation into Liver Chemistry Elevations: For patients with confirmed ALT or AST levels > 3 x ULN, the following evaluations should be performed:

1. Obtain a more detailed history of symptoms and prior and concurrent diseases
2. Obtain further history for concomitant drug use (including nonprescription medications, herbal and dietary supplement preparations), alcohol use, recreational drug use, and special diets
3. Obtain a history for exposure to environmental chemical agents and travel
4. Serology for viral hepatitis (hepatitis A virus [HAV] immunoglobulin M [IgM], hepatitis B surface antigen [HBsAg], hepatitis C virus [HCV] antibody, Cytomegalovirus [CMV] IgM, and EBV antibody panel)
5. Serology for autoimmune hepatitis (e.g., antinuclear antibody [ANA])

Additional liver evaluations, including gastroenterology/hepatology consultations, hepatic CT or MRI scans, may be performed at the discretion of the Investigator, in consultation with the Sponsor Medical Monitor and the study DSMB. Repetition of the above evaluations should be considered if a patient's ALT and/or AST levels reach 5 x ULN.

All routine liver function test results will be reviewed on an ongoing basis at the weekly safety review by the Medical Monitor.

All lab alerts for abnormal liver function tests must be promptly (within 48 hours of receipt) reviewed by the Investigator and Medical Monitors.

Lab alerts for abnormal liver chemistry tests will be issued for: 1) ALT or AST > 3 x ULN; 2) ALT or AST > 2 x baseline; 3) total bilirubin > ULN; 4) ALP > ULN. These alert levels are set to anticipate the risk of a combined elevation of aminotransferases and bilirubin as per the FDA Guidance referenced in [Section 8.5.1](#).

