#### **8.6.1 Stopping Rules for Liver Chemistry Elevations**

In the event of confirmed laboratory results meeting any of the following criteria, dosing of a patient with Study Drug will be stopped permanently:

1. ALT or AST  $> 8 \times \text{ULN}$ , which is confirmed
2. ALT or AST  $> 5 \times \text{ULN}$ , which is confirmed and persists for  $\geq 2$  weeks

3. ALT or AST > 3 x ULN (or the greater of 2 x Baseline value or 3 x ULN if the Baseline value was > ULN), which is confirmed **and** total bilirubin > 2 x ULN or INR > 1.5
4. ALT or AST > 3 x ULN (or the greater of 2 x Baseline value or 3 x ULN if the Baseline value was > ULN), which is confirmed, and the new appearance (i.e., onset coincides with the changes in hepatic enzymes) of fatigue, nausea, vomiting, right upper quadrant pain or tenderness, fever, rash, or eosinophilia (> ULN) felt by the Investigator to be potentially related to hepatic inflammation

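### INR is required only after ALT/AST > 3 x ULN is confirmed, so a weekly-dosed patient who already meets the INR stopping rule can receive one more dose first

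*Protocol*

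**What the plan says.** All references are to Protocol Amendment 4, the current version.

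- **Stopping rule.** Section 8.6.1, criterion 3, stops dosing permanently if ALT or AST above 3 x ULN is confirmed together with "total bilirubin > 2 x ULN or INR > 1.5". If baseline was above ULN, the enzyme threshold is the greater of 2 x baseline and 3 x ULN.
- **Confirmation.** After a first ALT or AST above the threshold, Section 8.5.1 says that "the initial measurement(s) should be confirmed as described in" Section 8.5. That means a new specimen before the next dose, ideally within 3 days.
- **After confirmation.** INR now appears, in the follow-up set: "ALT, AST, ALP, international normalized ratio [INR] and total bilirubin) retested at least once weekly", until ALT and AST are at or below 1.2 x ULN.
- **Symptoms of hepatic injury.** Section 8.5.1: "liver enzymes and bilirubin should be tested as soon as possible". INR is not named.
- **Panels.** In Appendix B the coagulation panel holds fibrinogen and plasminogen only. The chemistry panel includes bilirubin but not INR.
- **Dose hold.** Section 8.5: "In the event of an initial clinical laboratory result that meets a stopping criterion, patients must not be re-dosed until a confirmatory test result". It is the Study Medical Monitor who must have looked at that result. Patients who do not meet a stopping rule on retest may in general carry on.
- **Alerts.** Besides ALT or AST above 3 x ULN, the liver alert triggers are "ALT or AST > 2 x baseline; 3) total bilirubin > ULN; 4) ALP > ULN". Under Section 6.2.1 alerts "should be received by them within 2 days from sample collection".
- **Discretion.** Section 8.5: "The Investigator may interrupt or permanently discontinue study treatment for any medical reason including changes in clinical laboratory results".

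**The concern.** A stopping rule can be applied only if its inputs are measured. Criterion 3 has two alternative legs. The bilirubin leg can be evaluated from the same chemistry sample that shows the raised enzymes. The INR leg cannot, because up to and including confirmation no liver-related test has to include INR. The other triggers for INR are a minor bleed (Section 8.5.4) and a platelet count below 100,000/mm³ (Appendix E), and neither need coincide with a liver signal.

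Take a patient with ALT or AST above 3 and not above 8 x ULN, bilirubin not above 2 x ULN, no hepatic symptoms and INR unmeasured. On paper that patient meets no stopping criterion, so the compulsory hold in Section 8.5 does not apply. Section 8.5.1 has no hold of its own for confirmed ALT or AST above 3 x ULN. By contrast, Section 8.5.2 interrupts dosing on a confirmed renal alert.

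If that patient's INR is in fact above 1.5, a permanent stop has already been met but is not yet visible. With weekly dosing, another injection can fall due before the required INR is drawn. What is at stake is a delayed safety stop in an individual patient; no efficacy or power conclusion is affected.

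**Working it through.** The protocol gives no figure to reproduce. The check is a timetable, followed by a rough count.

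**Inputs**
- Cohort E doses every 7 days (Section 8.1), so doses fall on days 0, 7, 14 and so on.
- Trigger sample taken pre-dose on a dosing day: day 0 (assumption).
- Confirmatory draw within 3 days (Section 8.5, stated as the ideal): day 3.
- First required INR within 7 days of confirmation (Section 8.5.1): latest draw = 3 + 7 = day 10.
- Turnaround of 2 days, the figure Section 6.2.1 gives for lab alerts, assumed here to apply to INR. Same-day results are the other extreme.

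**Permitted days for the first INR draw: day 3 to day 10, that is 8 days**

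| Draw day | Result day, 2-day turnaround | Back by day 7? | Back by day 7 if same-day? |
|---|---|---|---|
| 3 | 5 | yes | yes |
| 4 | 6 | yes | yes |
| 5 | 7 | yes | yes |
| 6 | 8 | no | yes |
| 7 | 9 | no | yes |
| 8 | 10 | no | no |
| 9 | 11 | no | no |
| 10 | 12 | no | no |

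So 5 of the 8 permitted draw days (2-day turnaround) or 3 of the 8 (same-day) leave the day-7 dose exposed. This counts days; it is not a probability.

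**Sensitivity to the confirmation day.** For confirmation on day 1, 2, 3, 5 or 7, the latest first INR draw is day 8, 9, 10, 12 or 14. In every case exactly one Cohort E dose (day 7) lies between confirmation and that draw.

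**Other cohorts.** On the day-3 timetable the latest INR result is 10 + 2 = day 12. The next dose is on day 14 (Cohort D, or Cohorts A–C when the trigger was a mid-cycle sample) or day 28. No dose is exposed.

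**With INR on the confirmatory specimen.** Draw on day 3, result on day 3 + 2 = 5, and the full 48-hour review ends on day 5 + 2 = 7. No Cohort E dose falls between the day-0 dose and the INR draw, whichever of the tested confirmation days is used.

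**Number of patients.** The protocol gives no rates, so these are assumptions shown as a range.
- Confirmed ALT or AST above 3 x ULN in 1% to 5% of the 45 active Cohort E patients (Section 10.2): 45 x 0.01 = 0.45 to 45 x 0.05 = 2.25.
- Of those, 1% to 10% with INR above 1.5, bilirubin not above 2 x ULN and no symptoms: 0.45 x 0.01 = 0.0045 to 2.25 x 0.10 = 0.225.

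**The case against.** The strongest reply is that medical review is compulsory even though an INR is not. ALT or AST above 3 x ULN raises an alert, which the Investigator and Medical Monitors must review within 48 hours. The monitors agree on actions, and for an actionable alert instructions reach the site within 24 hours (Sections 6.2.1 and 8.5.1). The elevation must be confirmed before the next dose, so physicians will be looking at the patient before day 7, and any of them can order an INR or withhold the dose. This stands: the gap is possible, not inevitable. But no text tells them to do either.

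Second, Section 8.5.1 lists INR among the liver chemistry tests and speaks of retesting, which suggests an earlier INR. On that reading the routine 2-weekly or monthly liver tests would include it. Appendix B does not support this, since neither the chemistry nor the coagulation panel contains INR. If it was intended, the section and the appendix disagree and still need a correction.

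Third, the event is rare and the rates above are assumed. Warfarin, direct thrombin inhibitors and factor Xa inhibitors are excluded, and a patient with symptoms, higher bilirubin or enzymes above 8 x ULN falls under another leg of Section 8.6.1. This stands, and it limits the size of the problem.

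Fourth, the timetable depends on where the clock starts. If a day-3 confirmation is known only on day 5, the weekly retest could fall as late as 5 + 7 = day 12, with a result on day 14, which is Cohort D's next dosing day. That is fair, but a later start widens the gap and does not close it.

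Finally, the renal hold is a rule for a different organ, so the contrast with it is not in itself an error.

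**Conclusion.** The point holds. Under Amendment 4 the INR leg of a permanent stopping rule cannot be evaluated from any required liver test until after the enzyme elevation is confirmed, and in Cohort E one 20 mg dose can lawfully come before the first required INR. That result rests on a trigger sample taken on a dosing day and on the first INR being drawn late in its permitted week. It holds for every confirmation day tested from day 1 to day 7. Cohorts A–D are not exposed on the day-3 timetable, though Cohort D becomes borderline if the weekly clock starts when confirmation becomes known.

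The expected number of patients is well under one (about 0.005 to 0.23 on assumed rates), and the consequence is a delayed stop. The bilirubin leg works as written. The change is worth making because it costs almost nothing and removes the reliance on discretion for a mandatory stop.

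**What to change.** Add one sentence to Section 8.5.1, with a matching reference in the confirmation guidance of Section 8.5: *The confirmatory specimen for ALT or AST > 3 x ULN must also be tested for INR and total bilirubin, and both results must be reviewed against criterion 3 of Section 8.6.1 before the next dose is given.*

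The stopping thresholds and the scheduled panels in Appendix B stay as they are. The cost is one coagulation tube at a draw that already takes place, with no new visit. A weekly dose may have to wait a day or two for the INR result.
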